#### 1. INTRODUCTION

Inducible Heme Oxygenase (HO - 1), an enzyme critical for heme catabolism, is also involved in cellular response to oxidative stress. We have previously shown that induction of HO-1 expression in response to limb ischemia confers pulmonary cellular protection against oxidative stress suggesting a systemic factor; however, the mechanism of this protection is unclear. Our follow-up study showing that carbon monoxide (CO) the product of heme catabolism by HO-1, can mimic this protection suggests that CO itself may be the important active molecule. Recent animal work has independently shown that HO-1 induction may also influence cellular regeneration in the liver following partial hepatectomy. Independently, CO has emerged as growth-promoting signal molecule with anti-apoptotic effect that protects hepatocytes from hypoglycemia - induced cytotoxicity. Further, administration of CO significantly improved the survival of mice after initiation of fulminant hepatitis and enhances rapid and early hepatocytes proliferation after partial hepatectomy, when mice lacking functional HO-1 were unable to mount an appropriate regenerative response. Collectively, these data suggest that the heme oxygenase - CO offers either direct or indirect protection against cellular injury and may promote regeneration in the liver. In this proposal, we will directly test the hypothesis that HO-1 induction is critical to hepatic regeneration after partial hepatectomy. We will further test the relevance of this observation in human patients undergoing partial hepatectomy by measuring CO production and correlating this to parameters of liver regeneration. To achieve objective, we will pursue two specific aims: (1) we will monitor the extent of HO-1 induction (by measuring endogenous CO production) in relationship to the extent of hepatic resection (2) we will assess the production of CO in patients following liver resection and correlate these findings to the rate of liver regeneration and liver function. This research will establish a framework for understanding the role of HO-1 induction in liver regeneration and will provide a foundation for developing more effective approaches in enhancing hepatic regeneration and preventing liver failure after partial hepatectomy.

## 2. STUDY OBJECTIVE

The goal of this proposal is to elucidate the role of HO-1 induction in hepatic regeneration after partial hepatectomy (PH). There is a growing body of evidence that HO-1 induction through CO production has an important role in cellular protection and regeneration. To test this concept, we will monitor endogenous CO production in patients who undergo PH and analyze the relationship between CO production and hepatic regeneration. Using this approach, we will test the following two hypotheses: (1) HO-1 induction after PH is proportional to the extent of the surgical resection, and (2) failure to appropriately induce HO-1 is associated with impaired hepatic regeneration.

## 3. INVESTIGATIONAL PLAN

This is a University of Maryland Medical System multi-site study being done at University of Maryland Medical Center and UM Baltimore Washington Medical Center.

The study will monitor carbon monoxide production in patients undergoing liver resection and aims to identify the relationship between CO production and recovery after this resection.

Carbon monoxide will be checked from arterial blood gas obtained routinely as a part of the postoperative care as well as from the exhaled air of the patient through a CO detector commercially available and used as smokerlyzer helping people to stop smoking. The results of the surgical resection will be collected from the patient routinely ordered tests after liver resection including pathology of the resected part of the liver, laboratory and radiology tests.

The study duration for each individual patient is approximately 3 months +/- 2 weeks.

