Study Design:	Study design: Aim 1.1: The monitoring of exhaled CO is based on previous report of assessing exhaled CO in septic patients. Exhaled CO will be determined with an infrared CO analyzer with a sensitivity of 0.1 ppm at 4 hours and 24 hours after PH Aim 1.2: Arterial blood gas (ABG) will be collected from patients before liver resection, at 4 hours and 24 hours after PH. The ABG will be obtained through an arterial line usually placed as part of perioperative monitoring of the patient hemodynamic. This model was found accurate in reflecting HO-1 induction in previous study in patient receiving liver transplantation. Aim 1.3: FLR will be calculated through liver volumetric study from a pre-resectional CT scan. The operative note will be checked for operative details regarding the number of resected hepatic segments and pathological examination of the specimen will allow accurate weight of the resected specimen. According to the resected amount of hepatic parenchyma, three groups of patients will be created (<25%, 25-50% and >50% PH) history of smoking and intraoperative blood transfusion will be reported for each patient. Procedures and Methods - Protocol: For collecting exhaled air specimen, each
	patient will be instructed to exhale completely, and then

take a deep breath, hold it for 20 seconds, and breathe out through D shaped flatpak mouth piece attached to CO analyzer

 
Equipment:
 
A Micro+ CO monitor (Bedfont Scientific Ltd, Wales, England) will be used to analyze CO level in a single breath in exhaled air. The device will be used by applying Anti-bacterial filter and one-way valve for increased infection control.
 
The device has adjustable breath-hold countdown timer for patients who are unable to hold their breath. Calibration will be performed every 6 months as per manufacture recommendation. The device is able to detect and analyze CO concentration within a range of: 0-250 ppm with a sensitivity of 0.1 ppm and accuracy of ±2% in < 20 seconds.
 
Direct evaluation of the COHb level will be performed using an arterial blood gas analyzer (ABL 800 Flex, Radiometer, Copenhagen) and will be reported as % of the total Hb as well as calculated amount in mg/mL.
 

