#### Analyses:

All results will be collected in Excel Document. Analyses of groups based on the extent of liver resection and CO production. Results of different subgroups will be analyzed; comparison between groups will be performed by fisher test, paired and unpaired student t test, main Whitney test or ANOVA with repeated measurements when appropriate. Significance is defined as p<0.05.

Potential problems and alternative strategy: It is possible that HO-1 induction varies according to preoperative and intraoperative factors beside the patient own ability to induce HO-1. The most important known other factors are smoking and intraoperative blood transfusion will be reported in the study, however, other factors may exist and influence the result of this study. Preoperative factors may include preoperative use of chemotherapy and the presence of underlying liver cirrhosis. Intraoperative factors may include operative time and surgical technique (open or minimally invasive). In case of significance variance between patient s in the same group (same percentage of PH) Subgroup analysis including different variants (preoperative chemotherapy, perioperative

	blood transfusion and onen vorsus minimally
	blood transfusion and open versus minimally
	invasive technique) will be used to assess the
	effect of these factors.
Study Population:	125 participants enrolled locally; 125
	enrolled worldwide
Inclusion Criteria:	1-Patients plans to have partial liver
	resection for primary liver pathology or
	metastatic disease
	2-Patients able to comprehend and willing to
	sign the written consent form
Exclusion Criteria:	1-Patients with age less than 18 years
	2-Patients identified as part of the vulnerable
	populations as defined in the current
	application, except women with child bearing
	potential with negative pregnancy test
Study Treatment:	For Aim 1, after the patient's procedure, they
	will have to exhale into the device listed for
	collecting exhaled air specimen.
	For Aim 2, the patient's blood samples that
	are routinely collected after a hepatectomy
	will be used for analyzing serum protein,
	Albumin, AST and ALT, alkaline phosphatase,
	and bilirubin level.
	The duration of an individual's participation
	will be about 3 months +/- 2 weeks.
Study Procedures and Assessments:	Aim 1:
	Procedures and Methods
	- Protocol:
	For collecting exhaled air specimen, each
	patient will be instructed to exhale
	completely, and then

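### Two hospitals are pooled in unadjusted comparisons, with neither site nor calendar period in the analysis, so a site difference that goes with extent of resection or CO could confound the results.

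*Combined protocol and SAP*

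**What the plan says.** Section 3 (Investigational Plan) calls this a "multi-site study being done at University of Maryland Medical Center and UM Baltimore Washington Medical Center". The Protocol Summary gives 125 participants, with no split by hospital, and an overall duration of 15 years. Section 3 adds that "The study duration for each individual patient is approximately 3 months +/- 2 weeks".

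The statistical text is the same for both aims (Protocol Summary, Analyses and Statistical Analyses). Comparisons use "fisher test, paired and unpaired student t test, main Whitney test or ANOVA with repeated measurements when appropriate", and "Significance is defined as p<0.05". No model, stratification or sensitivity analysis involves site or calendar time.

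The paragraph on potential problems names smoking, transfusion, chemotherapy, cirrhosis, operative time and surgical technique. It plans subgroup analyses by chemotherapy, transfusion and technique only, and only if patients within an extent group vary significantly. Site and period appear in neither list.

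On measurement, the Protocol Summary names one breath-monitor model (accuracy ±2%) and one blood-gas analyser model. For the monitor it says "Calibration will be performed every 6 months as per manufacture recommendation". Outcomes come from routinely ordered tests (section 3), and no central laboratory or reference range is given.

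**The concern.** The study is observational, so nothing in the design balances extent of resection, underlying disease or surgical technique across the two hospitals. Three things can plausibly differ between them:

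- **Case mix.** The plan itself names technique, chemotherapy and cirrhosis as possible influences on HO-1 induction. Each may vary by hospital or by era.
- **Laboratory limits.** Time to normalization of liver tests, and the day-5 INR and bilirubin criterion, depend on what each laboratory calls normal.
- **Liver-failure grade.** The grade is set by the effect on clinical management, so it partly reflects local practice.

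Individual CO monitors or analysers are a fourth and weaker possibility. The text names models. It does not say how many units serve two hospitals, or what happens when one is replaced.

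At stake are the link between CO and extent (hypothesis 1) and the link between HO-1 induction and regeneration or morbidity (hypothesis 2). Site is known for every patient and is cheap to adjust for, yet the plan leaves it out.

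**Working it through.** The plan gives no power, SD, site split or between-site difference, so there is no figure of its own to reproduce. What follows illustrates the possible size. From the documents: two sites, N = 125, significance at 0.05 (taken as two-sided), three extent groups. All other inputs are assumptions.

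**Two-group illustration.** Assume no true effect of extent, a within-site SD of 1, and one site higher on CO by a fixed offset.

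Spurious difference = offset × (share of major resections done at site A − share of minor resections done at site A).

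- *Stronger imbalance*: 90 patients at A, 45% major; 35 at B, 15% major. Major: 40.5 + 5.25 = 45.75. Minor: 49.5 + 29.75 = 79.25. Shares at A: 40.5/45.75 = 0.885 and 49.5/79.25 = 0.625. Difference 0.261.
- *Milder imbalance*: 80 at A, 40% major; 45 at B, 25% major. Major: 32 + 11.25 = 43.25. Minor: 48 + 33.75 = 81.75. Shares at A: 0.740 and 0.587. Difference 0.153.

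Rejection rates come from simulating the ordinary pooled t test, with patient counts rounded to whole numbers:

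| Imbalance | Offset (SD) | Spurious difference (SD) | Rejects, no site term | Rejects, site term |
|---|---|---|---|---|
| Stronger | 0.3 | 0.08 | about 7% | about 5% |
| Stronger | 0.5 | 0.13 | about 10% | about 5% |
| Stronger | 1.0 | 0.26 | about 23% | about 5% |
| Milder | 0.3 | 0.05 | about 5.5% | about 5% |
| Milder | 0.5 | 0.08 | about 6.4% | about 5% |
| Milder | 1.0 | 0.15 | about 9.3% | about 5% |

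The site term makes the standard error of the extent effect about 4% larger in the stronger scenario and about 1% larger in the milder one.

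A shortcut that holds the SD at 1, P(|Z + bias/SE| > 1.96) with SE = √(1/n_major + 1/n_minor), gives 7%/11%/29% and 6%/7%/13%. It overstates the larger offsets because the site offset also inflates the pooled SD that the t test uses.

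**Three-group check.** This uses the plan's three extent groups (42/42/41 patients assumed), a one-way F test, offsets of 0.25/0.5/1.0 SD and 4,000 runs per scenario. Site-2 shares are given in the order <25%, 25-50%, >50%:

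- Shares 30/30/30%: 4.7% to 5.1%, so no inflation when site mix is the same in every group.
- Shares 40/30/20%: 5.6%, 6.0%, 9.8%.
- Shares 50/30/10%: 7.0%, 11.6%, 30.0%.
- With a site term: 4.6% to 5.3% in every scenario, including those with no offset.

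**Baseline.** Sections 6 and 7 collect CO before resection as well as at 4 and 24 hours. If a site adds a constant c to every reading, (post + c) − (pre + c) = post − pre, so the offset cancels in the change. It does not cancel in raw postoperative values. A proportional calibration difference, a case-mix difference or a site-dependent outcome definition also survives subtraction.

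**The case against.** The strongest reply is that the plan already contains controls. One monitor model and one analyser model are named, the monitor's stated accuracy is ±2%, and it is calibrated every 6 months. CO is measured preoperatively, and paired tests and repeated-measures ANOVA are on the list. Liver volume is expressed as a percentage of the patient's own preoperative volume. Both hospitals belong to one health system, and the plan admits that unlisted factors may matter.

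Much of this stands. A reader might infer that the two sites use different CO devices; the documents do not support that. What remains open is the number of units, drift between calibrations and replacement. A reader might also take the 15 years as the enrolment period. It is the overall study duration, and the documents do not say how long recruitment lasts or when each hospital joined. The rate of 125/15 = 8.3 patients a year holds only if enrolment fills the whole period.

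The reply does not dispose of the point. The plan does not commit to change from baseline for comparisons between groups, and the endpoint list in the Protocol Summary gives CO only at 4 and 24 hours. Laboratory limits, management-based grades and case mix do not depend on the devices. The conditional subgroup analyses do not include site.

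It is also fair to say that stratified tests may be unstable in sparse complication or liver-failure tables, and that a full period adjustment in every model would be more than the evidence here requires.

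**Conclusion.** The point holds as an uncontrolled risk. It is tempting to conclude that pooling biases both hypotheses, but the documents do not support that. Confounding requires site to be related both to extent (or CO) and to the outcome, and they give no site split, case mix by site or between-site difference.

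If such an imbalance exists, the illustration puts the false-positive rate of a nominal 5% comparison at about 5.5% to 23%, depending on imbalance and offset. With a mild imbalance and an offset up to 0.5 SD it stays close to nominal; with no imbalance there is no inflation. These figures concern the extent comparison only. No size has been worked out for the link between CO and outcome, or for a calendar-period effect. A site term restores about 5% throughout at little cost, so adding it is worthwhile even though the bias is not demonstrated.

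**What to change.** - Include site as a fixed term in the comparisons of CO and of continuous outcomes.
- Analyse CO and COHb as change from the preoperative value, or adjusted for it, and say so for the between-group comparisons.
- Use a site-stratified (Cochran-Mantel-Haenszel) test in place of Fisher's test where counts allow. Where tables are too sparse, keep Fisher's test and report results by site descriptively.
- Express laboratory values that are judged by an upper limit as multiples of that hospital's upper limit.
- Record the monitor and analyser unit used for each sample, starting now, because this is hard to recover later.
- Examine calendar period in a sensitivity analysis.

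The cost is one or two degrees of freedom, a standard error about 1-4% larger in the scenarios above, possible instability in sparse complication tables, and one data field. No new patients or visits are needed.

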## 4. STUDY TREATMENT

Subjects who met all inclusion and exclusion criteria according to the data collected from medical records will have their carbon monoxide checked from arterial blood gas obtained as part of routine post-operative care, as well as from exhaled air measured through a CO detector. This study involves prospective data collection that does no interfere with treatment plan of participants.

## 5. STUDY POPULATION

The populations to be included are as follows:

Gender: Female, Male

Ages: 18-88 years (adult)

Race/Ethnicity: All Races Included

Languages: English

No vulnerable populations are being targeted.

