## 5.2 Exclusion Criteria

-Patients with age less than 18 years

-Patients identified as part of the vulnerable populations as defined in the current application, except women with child bearing potential with negative pregnancy test

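### Aim 2 relates CO induction to regeneration and morbidity by unadjusted tests only; neither age nor the confounders the plan itself names enter any model

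*Combined protocol and SAP*

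**What the plan says.** Section 5 of the protocol gives the age range as "Ages: 18-88 years (adult", and the only age rule in Section 5.2 is the exclusion "Patients with age less than 18 years". Age must therefore be known for every patient at screening.

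Section 2 states the second hypothesis: "failure to appropriately induce HO-1 is associated with impaired hepatic regeneration". Aim 2.1 tests it against CT volumetry at one and three months and liver function tests. Aim 2.2 relates HO-1 induction to complications within 30 days.

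The Analyses part of the Protocol Summary describes "Analyses of groups based on the extent of liver resection and CO production", compared by Fisher's test or by "paired and unpaired student t test, main Whitney test or ANOVA with repeated measurements when appropriate". It adds "Significance is defined as p<0.05". The Statistical Analyses entry repeats the same text for Aim 1 and Aim 2. Neither document section contains a regression, an analysis of covariance, matching or stratification by age.

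The paragraph on potential problems does recognise confounding. It ranks smoking and intraoperative transfusion as the most important other factors. It continues "Preoperative factors may include preoperative use of chemotherapy and the presence of underlying liver cirrhosis", adds operative time and surgical technique, and concedes that further factors may exist. Its only remedy is a subgroup analysis by chemotherapy, transfusion and open versus minimally invasive technique, carried out only if patients within a resection group vary significantly.

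**The concern.** CO induction is a patient characteristic, so patients with high and low CO can differ in other ways that bear on regrowth and complications. A crude test cannot tell a shared cause from an HO-1 association. Age is a natural candidate for a shared cause: the permitted range spans 88 − 18 = 70 years, age is recorded for everyone, and nothing in the plan takes it into account. Grouping by extent of resection (<25%, 25-50%, >50%) does not balance age within a group.

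The gap is wider than age. The conditional subgroup list leaves out smoking, cirrhosis and operative time, all of which the plan names, and a subgroup split is not an adjusted estimate.

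At stake is how an Aim 2 result can be read. Section 1 sets out to test whether HO-1 induction is critical to regeneration. A crude association could be produced, enlarged, masked or reversed by a factor that the plan could have held constant at little cost.

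**Working it through.** **Inputs from the documents.** n = 125 ("125 participants enrolled locally; 125", Study Population entry of the Protocol Summary) and alpha = 0.05. Sidedness is not stated; two-sided is assumed here.

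**The plan's own figure.** The 125 cannot be reproduced, because no effect size, standard deviation, power or dropout rate is given. For orientation only, the correlation detectable with 80% power is tanh((1.960 + 0.842)/√122) = 0.248.

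**Inputs that are assumptions.** The documents give no correlation of age with CO or with any outcome. I let each take the value a, from 0.1 to 0.5, and assume no HO-1 effect.

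**Step 1.** With no direct effect, the crude CO-outcome correlation is r = r(age, CO) × r(age, outcome) = a².

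**Step 2.** The expected Fisher z statistic is s = atanh(r) × √(n − 3), with √122 = 11.045 at n = 125.

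**Step 3.** The rejection rate is Φ(s − 1.96) + Φ(−s − 1.96).

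| a | r = a² | s (n = 125) | Rejection, n = 125 | Rejection, n = 100 |
|---|---|---|---|---|
| 0.1 | 0.01 | 0.110 | 5.1% | 5.1% |
| 0.2 | 0.04 | 0.442 | 7.3% | 6.8% |
| 0.3 | 0.09 | 0.997 | 16.9% | 14.4% |
| 0.4 | 0.16 | 1.783 | 43.0% | 35.6% |
| 0.5 | 0.25 | 2.821 | 80.5% | 71.1% |

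The n = 100 column is illustrative, for the case where some patients lack a follow-up CT.

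**Unequal correlations.** At 0.1 and 0.3, r = 0.03 and s = 0.331, so the rate is Φ(−1.629) + Φ(−2.291) = about 6.3%.

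**Does adjustment work?** In a simulation of 20,000 studies of 125 patients, the unadjusted test rejected in 7.4%, 16.9%, 43.5% and 81.1% at a = 0.2, 0.3, 0.4 and 0.5. The partial correlation given age rejected in 5.1%, 5.2%, 5.2% and 5.0%.

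**Limits of the calculation.** It covers a correlation test on a continuous outcome with every patient analysable. The plan lists group comparisons, and no corresponding figure was calculated for morbidity. The table shows how the mechanism scales; it is not an estimate of this study's error rate.

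**The case against.** The strongest case on the other side has five parts.

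- **The premise is not documented.** Nowhere do the documents say that age affects CO, regeneration or morbidity. This stands: the confounding is possible, not shown.
- **The direction is open.** A reader might infer that age biases the result toward the second hypothesis and so produces false support. That needs CO to fall with age. If instead older patients were transfused more and transfusion raised CO, the bias would run the other way. The documents settle neither sign, so this inference is not supported.
- **The size may be trivial.** At correlations of 0.2 or below the rejection rate is at most 7.3%, and the figures are not for the planned tests. This stands.
- **The hypothesis is worded as an association, and a marker can predict while standing in for age.** This is correct as far as the wording goes. It does not protect the stronger reading in Section 1, and reporting both crude and adjusted estimates serves either purpose.
- **Age is singled out although the plan discusses confounding and ranks other factors higher.** This stands in part. Adjusting for age and extent alone would miss smoking and transfusion. The answer is one model containing all of them.

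None of this supplies an adjusted analysis, which the plan lacks for every factor.

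**Conclusion.** The point holds as a weakness in the choice of analysis: a non-randomised exposure is compared on outcome by crude tests alone, with age overlooked and the plan's own named factors left unadjusted. Age need not affect CO, regeneration and morbidity together; a relation with CO and with one outcome is enough to confound that one comparison.

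The consequence ranges from negligible (5.1% at assumed correlations of 0.1, 7.3% at 0.2) to serious (16.9% at 0.3, 43.0% at 0.4), against a nominal 5%. These figures assume two-sided testing, 125 analysable patients, equal correlations and no HO-1 effect. They do not show that the study's results will be biased, and they say nothing about direction.

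A reader might also take the wide age range as a flaw in itself. It is not: it is an eligibility range, it does not tell us the age spread of those enrolled, and the matter is one of analysis.

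**What to change.** Prespecify for Aim 2:

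- a regression of CT regeneration on CO, and a logistic regression of morbidity on CO, with the morbidity event defined in advance;
- in both, adjustment for extent of resection, age in years as a continuous covariate, smoking and intraoperative transfusion, the last two being the factors the plan ranks highest;
- a penalised (Firth) fit for the logistic model if events are few;
- the CO estimate with its confidence interval, both crude and adjusted.

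The crude tests can stay as descriptive results, and the remaining named factors can be examined as sensitivity analyses if the number of events allows.

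The cost is a few degrees of freedom out of 125 patients and some added analysis work, since the plan contains no regression at present. No new data are needed: age is required for eligibility, extent defines the planned groups, and smoking and transfusion are already to be reported for each patient.
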